Dry eye disease (DED) affects up to 20% of the population in North America.¹ Clinically there is a plethora of irritation symptoms associated with DED, which includes ocular burning, foreign body sensation, soreness, stinging, scratchiness, photophobia and blurred vision. In 1995, the National Eye Institute workshops (in USA), defined dry eye as “a disorder of the tear film due to tear deficiency or excessive evaporation that causes damage to the interpalpebral ocular surface and is associated with symptoms of discomfort”.² Recent studies point to the importance of the meibomian glands of the eyelids to avoid DED. Meibomian glands are located in the upper and lower eyelids and produce an oily substance that helps stop the water in the tears from evaporating, thus helping to prevent dry eyes. Meibomian gland dysfunction (MGD) is defined as “a chronic, diffuse abnormality of the meibomian glands, commonly characterized by terminal duct obstruction and/or qualitative/quantitative changes in the glandular secretion. It may result in changes of the tear film, symptoms of eye irritation, clinically apparent inflammation, and ocular surface disease.”³ The term “posterior blepharitis” is often used synonymously with MGD, however, in its early stages, MGD is not always associated with inflammation of the eyelid. The symptoms of MGD are a consequence of a reduced quantity and/or quality of meibum that is supplied to the ocular surface. The terminal ends of the ducts of the meibomian glands can become blocked with keratinized cells. Importantly, such obstruction of the duct can lead to ductal dilatation and loss of secretory cells in the acini of the gland.⁴ Blocked terminal ducts reduce the quantity of meibum produced by the gland, and are also, most likely, responsible for affecting its lipid composition deleteriously. In MGD, there is a clear tendency for more branched chain fatty acids and cholesterol in the meibum, which result in a more waxy and viscous

character.

Fig 1. Meibomian glands are the oil- producing glands located in both the upper and lower eyelids. The glands normally slowly release oil into the tear film. This oil helps to stop the water in the tears from evaporating, thus helping to prevent dry eyes.

(picture: <http://contactlens.org.nz>)

Systematic studies of the epidemiology of MGD have been hampered by difficulties in definition and lack of standardized tools for clinical assessment. Moreover, the specialized tests required to identify MGD in an early stage are not appropriate for use in population- based epidemiological studies.⁵ However, some trends are clear, i.e., Asian populations appear to have a much higher prevalence of MGD than do Caucasians.⁵ A number of factors have been identified that coexist with MGD. Although causal links have not been proven, plausible mechanisms exist for

connecting them with the pathophysiology of MGD, i.e., anterior blepharitis, contact lens use, Demodex mite infestation, and DED.⁵ In addition, hormonal conditions, including menopause and androgen deficiency, rosacea, psoriasis, atopy, and hypertension may contribute to the illness.⁵ In

Tørreøynekliviken (TØK), we have access

to state-of-the-art equipment to diagnose various subgroups of DED. This gives us an opportunity to assess the relative importance of MGD in our cohort of DED patients. Our studies so far reveal that about 80 % of our patients have DED caused by MGD. The large number of patients suffering from MGD has encouraged us to compare various treatment options to optimize future treatment of the disease.

The Significance of Studying Dry Eye Disease

The prevalence of DED in the Norwegian population is unknown, but based on epidemiological studies abroad, probably about 1 million Norwegians suffer from DED in one form or another. Age is an important risk factor for DED. Therefore, the prevalence of DED is expected to increase in the years to come as population ageing is unprecedented, without parallel in human history.⁶ Thus, research on DED is important for a large proportion of our population. Sadly, it has been an underprioritized field of research in the Nordic Region in sharp contrast to many other

countries. For example, at the Department of Ophthalmology, Harvard Medical School, DED is a highly prioritized field with several research groups working on improved treatment modalities. Research on DED holds the prospect to significantly improve quality of life for hundreds of thousand people in Norway. In addition, research on DED is critical to maximize the clinical outcome of some of the most severe forms of visual impairment that necessitate ocular surface stem cell treatment and/or corneal transplantations. Without an adequate tear film, these transplants will inevitably fail. Therefore, research on DED has the potential to help patients with the most severe visual impairments, either directly (in the event of keratinizing DED) or indirectly by enhancing the clinical results of other surgical procedures. In the light of DED being both a widespread disease and having huge implications for maximizing outcome of several diseases and treatments in ophthalmology, several members of our research group has taken measures to contribute to lessening DED in the Norwegian population. One example is the establishment of the Norwegian Dry Eye Clinic, which is the first specialized clinic for DED in Scandinavia.

Treatment Options for Meibomian Gland Dysfunction

There are several treatment options for MGD, but yet no consensus on the best approach. Lid scrubs using for example mild shampoo, eyelid massage and warm compresses of the eyelids, belong to the basic therapy. In addition, a large number of medications have been suggested over the past years for more severe forms of MGD. Comparative studies between possible treatment strategies are warranted to be able to conclude on the best available options.

Basic Therapy

Good eyelid hygiene, warming and massage are considered an effective mainstream therapy for MGD and blepharitis, in spite of the lack of standardization of the technique as well as the uncertainty about patient compliance. Studies comparing different methods of mainstream 4 therapy, such as eyelid warming, would allow evidence-based recommendations. The diversity of recommendations for such basic treatment is exemplified by the advice given in two leading textbooks of ophthalmology:

- “Warm wet face cloth for 5 minutes once or twice a day, and massage upper and lower lid (Moorfields Manual)”
- “Warm compresses for 15 minutes four times per day, and clean with wet cotton bud and mild (baby) shampoo (Will’s Eye Manual)”.

Recent advances

Recently, there have been two alternatives to the conventional, but somewhat unstandardized

basic treatment. Blephasteam® (Thea, France), which is eyelid-warming goggles (patented medical device) is one such option. The goggles are designed to deliver standardized conditions of moist heat therapy for 10 minutes in order to melt meibomian secretion. This dual action (moist and heat) unblocks the meibomian glands. The principal effect of this device is to improve the thickness and quality of the lipid layer of the tear film, thus enhancing tear function. THERA°PEARL Eye Mask (Bausch & Lomb Inc., New York, USA), is another mask with similar functions. It is heated in a microwave and placed on the eyelids to melt the meibomian secretion.

Additional Therapy (a Selection)

Antibiotics. A number of topical and systemic antibiotics with effect against lid-related bacteria are available. Solid evidence, however, based on randomized controlled clinical trials is lacking. This makes guidance of antimicrobial management of MGD difficult. Tetracyclines are widely used in several ocular surface diseases, including ocular rosacea, corneal angiogenesis blepharitis, recurrent erosions, and DED. These components may be helpful for blocking the vicious-circle characteristics of dry eye disease and severe MGD through 1) anti-inflammatory and anti-apoptotic properties and 2) by counteracting the free fatty acid accumulation known to be responsible for development of MGD. Despite several studies on oral tetracyclines in the treatment of MGD, additional comparative studies against other therapies are needed.⁷ Interestingly, one such recent study demonstrated better effects of using a macrolide (azithromycin) compared to applying a tetracycline (doxycycline) for the treatment of MGD.⁸

Immunosuppressive medication. Most studies involving topical cyclosporine are small in sample size.⁹⁻¹¹ Interpretation of some of the studies is somewhat challenging due to the influence of a reduced Schirmer score or the presence of ocular rosacea. A recent, randomized double-masked study on the use of topical cyclosporine confirms its potential role in the treatment of MGD.¹² However, there are no comparative studies of a combined approach using the presumptive best choice of antibiotics and cyclosporine compared with antibiotics alone.

Ocular protection: In addition to providing the ocular surface with moist, ocular protection in the forms of drops has proved advantageous. Sodium hyaluronate and disaccharides have been included in eye drops with the aim of increasing ocular protection. Sodium hyaluronate containing solutions have been demonstrated to result in improvement in dry eye in patients compared to other lubricant solutions in several studies.^{13,14} Naturally occurring disaccharides, which are a major component in Thealoz, are used with the purpose of protecting the cells of the cornea and conjunctiva as well as to give resistance to dryness. Thealoz has proved successful in clinical studies.^{15,16}

Study Description

Aims: To compare the effects of THERA°PEARL Eye Mask with the use of Blephasteam®.

Study Design

All the studies will be conducted based on written consent of the patients. Moreover, they will be performed in accordance with the tenets of the Helsinki Declaration and after approval from the Regional Ethics Committee as well as. If the patients encounter any problems during the study, they will be examined, irrespective of the planned follow-ups. The patients are free to quit the study at any time for any reason.

To answer our aim, we have, in brief, chosen the following study design:

1) THERA°PEARL Eye Mask versus treatment with Blephasteam®. In both groups, 60 patients with MGD are enrolled. We aim to make the two groups comparable as to the severity of the disease, age, and gender. The patients will be examined before the treatment and after 3 months, and 6 months. Treatment for both groups will be according to the manufacturer. All the analyses mentioned in the section *analyses* are planned to be included at every examination. Inclusion criteria: Meibomian gland dysfunction and candidate for eyelid heat therapy. Diagnosis of at least mild severity will be based upon recommendation by the diagnostic subcommittee of the International Workshop on Meibomian Gland Dysfunction, as seen in Table 1.

Ocular Surface Disease Index (OSDI)	>12
Quality or expressibility score	≤20 years old: >1 >20 years old: ≥1
Non-invasive tear film break-up time (NITBUT)	<10 s in at least one eye
Schirmer-1 test	>5 mm after 5 min in at least one eye

Exclusion criteria: Glaucoma, ocular allergy, autoimmune disease, contact lens-wear during study, current punctal plugging, pregnant/lactating, candidate for topical anti-inflammatory therapy, or cicatricial MGD.

Analyses

McMonnies Dry Eye Questionnaire. The McMonnies Dry Eye Questionnaire has been considered to be the "gold standard" for examining dry eye symptoms. The validity of the theory behind the questions and the questionnaire's usefulness in clinical settings has been demonstrated in numerous research articles.¹⁷ In addition, Ocular Surface Disease Index [OSDI] will be applied.¹⁸

Slit lamp examination. The cornea will be evaluated for the presence of active inflammation or structural change. The iris and anterior chamber will be assessed for sign of inflammation, whereas the eyelids will be evaluated for sign of Meibomian gland dysfunction with grading of the quality, expressibility, and volume of gland secretion, according to the Bron/Foulks scoring system.¹⁹

Tear film quantity and quality. RTVue (Optovue Inc, Fremont, CA) (http://www.optovue.com/wp-content/uploads/RTVue-Single-Sheet-Brochure_RevF.pdf) is the most comprehensive High Definition Ocular Coherence Tomography (OCT) system available today.²⁰ The Cornea Anterior Module unit for the RTVue system provides a rapid, non-contact, non-invasive method for producing high-quality images (5 micrometer resolution) that enable measurements of the tear meniscus. The overall tear volume can quite well be predicted by measuring the tear meniscus size^{21,22} as the meniscus contains 75% to 90% of the tear volume²³. Its size is related to the tear secretion rate²³ and the tear stability.²⁴ In addition, the Schirmer test, a traditional tear production measurement, will be applied with and without anesthesia. TBUT (fluorescein break-up time) will be used to test the quality of the tear film. TBUT will be measured after instilling 5 uL of a 2% sodium fluorescein solution. The average of three consecutive break-up times manually determined with a stopwatch will be calculated. Corneal staining will be evaluated under cobalt blue illumination 2.5 to 3.0 minutes after fluorescein instillation. The staining amplitude will be measured according to the National Eye Institute (NEI)/Industry Workshop scale.² Likewise, conjunctival staining will be investigated 2.5 to 3.0 minutes after 10 uL of a 1% sodium lissamine green dye is instilled. Conjunctival staining amplitude will be assessed in accordance with the NEI/Industry Workshop scale.²

Tear film osmolarity. TearLab TM Osmolarity system (TearLab, San Diego, CA) will be used. It requires a very small volume of tears (50nL), which will be collected at the inferior lateral meniscus.

Luminex. A multiplex Luminex® bead-based assay will be used to analyze ten cytokines (interleukin 1 α [IL-1 α], IL-1 β , IL-1ra, IL-4, IL-6, IL-8, IL-10, IL-13, monocyte chemoattractant protein-1 [MCP-1], and tumor necrosis factor- α [TNF- α]) and five metalloproteinases (MMPs) (MMP-1, MMP-2, MMP-7, MMP-9, and MMP-10). The Luminex bead-based assay is based on the principle of flow cytometry. The system allows us to simultaneously measure numerous analytes in a single microplate well, using very small sample volumes²⁵ while for many cytokines achieving excellent correlations to individual Enzyme-linked immunosorbent assay (ELISA).²⁶ Recently, Luminex has been used to measure the cytokine content in tear

samples collected with capillary tubes^{27,28} or Schirmer strips.²⁹ The analyses will be performed at the Department of Medical Biochemistry, Oslo University Norway. The content of cytokines and MMPs will guide us in the evaluation of the effectiveness the treatment. Moreover, it will shed light on the pathological mechanisms. As the important role of inflammation in DED has gained considerable scientific support recent years, a Luminex based approach seems pertinent in a clinical setting.

Confocal microscopy. Heidelberg Retina Tomograph with Rostock corneal module (<http://www.heidelbergengineering.com/products/hrt-glaucoma-module/cornea-module/>) is considered a state-of-the art diagnostic tool to evaluate the cornea at high magnification. In the present proposal, the density of presumed inflammatory cells in the central and peripheral cornea, subbasal nerve fibers, and epithelial wing cells will be investigated. Two independent investigators will evaluate the confocal pictures, and inter-observer variability will be measured to further assess the robustness of the method.

Keratograph 5M. Keratograph 5M (Oculus, Germany) technology will be used to enable meibography, which is a novel *in vivo* technique that provides photographic documentation of the meibomian gland, including the ducts and acini, under specialized illumination. *In vivo* confocal microscopy has the advantage of very high resolution, but at the expense of the overview. Both detailed analyses of selected glands and an overview of the general health of all the glands in the eyelids are important to be able to decide upon the best treatment strategies.

Integrative approach. The Dry Eye WorkShop (DEWS) severity scale³⁰ will be used as it integrates the values derived from the following analyses in one single score: tear osmolarity, Schirmer tests, TBUT, corneal staining, meibomian score, conjunctival staining, and OSDI.

Data Management and Statistical Analysis Plan

All data will be stored in a special electronic medical record system built for management of dry eye disease. The extraction of the patient data from the system database will be carried out according to guidelines by the Regional Ethical Committee and the Norwegian Data Protection Agency. The dataset will be de-identified prior to any statistical analyses.

All data will be checked for normality to determine the appropriate parametric or non-parametric test. To test for differences among groups, relevant Chi square test, one-way analysis of variance (ANOVA) and Kruskal–Wallis equality- of-populations rank test will be used. Where there is difference among groups, relevant Student's t test or Wilcoxon rank sum test will be performed. Chi square test will be used to evaluate the differences in the primary and secondary outcomes between groups. Logistic regression will be used to adjust for baseline differences. Statistically significant difference is based on 0.05 level of significance. All analyses will be performed with SPSS software, version 24 (IBM Corp., NY, USA).

Missing data will be handled with last observation carried forward.

Zero-hypotheses: Blephasteam® (Spectrum Thea Pharmaceuticals LTD, Macclesfield, UK) and THERA°PEARL Eye Mask (Bausch & Lomb Inc., New York, USA) differ by a clinically relevant amount. Type I error rate of 0.05 and power (type II error rate) 0.20. There are many parameters that will be measured in the study, the primary being tear film break-up time (TFBUT).

Originality and Scientific/Clinical Value

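### No standard harm question, explicit lid-skin item or per-device harm summary is planned, so lid-skin effects and short-lived device problems would be undercounted

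*Combined protocol and SAP*

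**What the plan says.** **Unplanned problems.** Under Study Design the protocol states: "If the patients encounter any problems during the study, they will be examined, irrespective of the planned follow-ups". It then says that patients may leave the study whenever they wish. The available text has no definition of an adverse event, no standard question, no form for the unscheduled examination and no rule for recording why someone stopped.

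**Scheduled visits.** "The patients will be examined before the treatment and after 3 months, and 6 months". Their content is set by one sentence: "All the analyses mentioned in the section *analyses* are planned to be included at every examination".

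**What those visits look at.** In the Analyses section the slit-lamp item covers the front of the eye: "The cornea will be evaluated for the presence of active inflammation or structural change", and "The iris and anterior chamber will be assessed for sign of inflammation". For the lids, "the eyelids will be evaluated for sign of Meibomian gland dysfunction with grading of the quality, expressibility, and volume of gland secretion". Staining is also scheduled ("Corneal staining will be evaluated under cobalt blue illumination 2.5 to 3.0 minutes after fluorescein instillation", plus conjunctival staining), as are the OSDI and McMonnies questionnaires, confocal microscopy, and tear cytokines and metalloproteinases.

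**The devices.** The Recent advances section describes goggles that deliver standardised moist heat for 10 minutes, and a mask: "It is heated in a microwave and placed on the eyelids to melt the meibomian secretion". Study Design says only that treatment follows the manufacturer.

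**Analysis.** The Data Management and Statistical Analysis Plan names tear film break-up time as primary, does not list the secondary outcomes, names no harm outcome, and fills missing data by last observation carried forward.

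**The concern.** Both devices put heat on the eyelids. The lid examination has no explicit item for the lid skin, and the first scheduled look after baseline is at 3 months. A patient who had redness or soreness of the lids in the second week, did not contact the clinic, and either recovered or stopped using the device would leave no trace as a harm. If that patient left the study, an earlier value would be carried forward into the efficacy analysis, and the plan does not require the reason for leaving to be recorded.

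The Basic Therapy section says that studies comparing ways of warming the eyelids would allow evidence-based recommendations. A reader choosing between two devices will want to know how often each caused trouble. From volunteered reports, a low count cannot be told apart from low reporting.

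**Working it through.** **Step 1: what each planned element can detect.**

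| Planned element | Both arms, every visit? | Picks up | Does not pick up |
|---|---|---|---|
| Examination when the patient has a problem | No; depends on the patient | Whatever the patient raises | Anything not raised |
| Slit lamp: cornea, iris, anterior chamber | Yes | Inflammation or corneal change present at the visit | Events resolved before the visit |
| Slit lamp: eyelids | Yes | Signs of MGD, gland secretion grades | Lid skin, as an explicit item |
| Staining, OSDI, McMonnies | Yes | Surface damage and dry-eye symptoms | Whether the device was the cause; stopping and why |
| Confocal microscopy, tear cytokines | Yes | Corneal cells and nerves, inflammatory markers | Lid effects; stopping and why |

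Staining and OSDI feed the DEWS severity score (Integrative approach), and the tear markers are there to help judge effectiveness. A worse value on these measures may mean harm or simply lack of effect. The corneal, iris and anterior-chamber findings have no stated role in the analysis.

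**Step 2: is there a planned figure to reproduce?** No. The plan gives no harm rate, capture rate or harm comparison. The only input from the documents is n = 60 per group (Study Design). The harm risks and capture fractions below are assumptions, shown as a range.

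**Step 3: what zero recorded events would mean in one arm.** If a fraction r of events is captured, the recorded risk is r × p. With 0 of 60 recorded, the one-sided 95% upper bound on the recorded risk is 1 − 0.05^(1/60) = 0.0487. The bound on the true risk p is that value divided by r:

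- r = 1: 4.9%
- r = 0.5 (assumed): 0.0487 / 0.5 = 9.7%
- r = 0.25 (assumed): 0.0487 / 0.25 = 19.5%

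This takes all 60 patients as observed; dropout would widen every bound.

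**Step 4: chance of recording at least one event in an arm**, 1 − (1 − r × p)^60:

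| Assumed true risk p | r = 1 | r = 0.5 | r = 0.25 |
|---|---|---|---|
| 1% | 45% | 26% | 14% |
| 3% | 84% | 60% | 36% |
| 5% | 95% | 78% | 53% |
| 10% | 99.8% | 95% | 78% |

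**Step 5: could full capture support a formal comparison?** For assumed risks of 2% and 10% with 60 per arm (two-sided 0.05), power is 45% by the normal approximation and 28% by Fisher's exact test. With half capture it falls to 25% and 5%. About 138 per arm would be needed for 80% power. Better collection therefore gives a trustworthy description, not a powered test.

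**The case against.** The strongest objection is that the plan does look for harm without waiting for the patient. The same corneal, iris, anterior-chamber, staining and symptom assessments are made in both arms at 3 and 6 months, and confocal microscopy adds corneal inflammatory-cell density. **This stands.** A reader might infer that no harm is seen unless a patient comes forward; the Analyses section contradicts that. These assessments do not close the gap, because they are snapshots, are not designated as safety, do not explicitly cover lid skin and do not ask about stopping.

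Further points on the other side:

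- **Lid margin.** The introduction says that MGD may involve visible inflammation, and the cited grading system may cover the margin. Visible lid inflammation at a visit might be noted as a sign of MGD. This stands in part: only the lack of an explicit lid-skin item is certain.
- **Device setting.** A reader might infer unsupervised use at home, or that under-reporting would differ between the devices. The documents do not support either. They say that one mask is heated in a microwave, not by whom or where, and that use follows the manufacturer.
- **Purpose.** The remark in the background about concluding on the best options concerns MGD treatments in general. The stated aim is to compare effects, and no safety claim is planned.
- **Records.** All data go into an electronic medical record, so an unscheduled examination may well leave an entry. Nothing plans to extract or tabulate it.
- **Size.** The capture fractions and risks are assumed, and sample size limits a harm comparison as much as ascertainment does. Both are true, and they are why the results should be labelled descriptive.
- **Available text.** Two parts of the combined document were not available for this review, so absence is judged on the rest.

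**Conclusion.** The concern holds in a limited form. In the available text, device problems as such are picked up only through examinations that the patient initiates. The scheduled visits measure disease status in both arms and would show some ocular-surface harm present on the day, but none of it is designated or analysed as safety. Lid-skin effects and problems that resolve between visits would be undercounted, and no harm summary per device would accompany the efficacy comparison.

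On size, zero events among 60 is compatible with a true risk of up to 4.9% under full capture, about 9.7% if half of events are volunteered and about 19.5% if a quarter are. The first figure depends only on n = 60 with everyone observed; the other two rest on assumed capture fractions that the documents neither give nor exclude.

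A reader might go further and infer that the trial would declare one device safe, or that better collection would deliver a powered comparison. The documents plan no safety conclusion, and step 5 rules out the second reading for risks such as 2% and 10%. The tear film break-up time comparison is not invalidated by this point. The change is a cheap improvement that should be made.

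**What to change.** Within the existing design:

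1. At the 3- and 6-month visits, ask every patient in both arms the same fixed question about problems since the last visit, including whether device use was stopped or reduced and why. Ask it before device use is otherwise discussed.
2. Add an explicit lid-skin and lid-margin item to the slit-lamp examination, recorded at baseline too so that change can be seen.
3. Record unscheduled examinations on the same form, with date, device and outcome.
4. Report, per device and with confidence intervals, the number of patients with at least one event and the number who stopped because of one. Label the table descriptive and place it beside the primary result.
5. State which of the existing corneal, iris, anterior-chamber and staining findings will also be summarised as safety.

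The cost is one short form, a wording change to an examination already planned, and one table. No extra visit, patient or change of treatment is needed. The downside is a few minutes per visit and more minor events on record.

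### The protocol specifies no random, concealed, concurrent allocation to the two devices, so a difference in break-up time, or the lack of one, could not be firmly attributed to the device

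*Combined protocol and SAP*

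**What the plan says.** The Study Description gives one aim: "To compare the effects of THERA°PEARL Eye Mask with the use of Blephasteam". Under Study Design, "In both groups, 60 patients with MGD are enrolled", and on the make-up of the groups, "We aim to make the two groups comparable as to the severity of the disease, age, and gender". The follow-up is stated as "The patients will be examined before the treatment and after 3 months, and 6 months".

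The Data Management and Statistical Analysis Plan names break-up time as the primary parameter. It lists unadjusted tests (chi-square, ANOVA, Kruskal–Wallis, t test, Wilcoxon rank sum) and one form of adjustment: "Logistic regression will be used to adjust for baseline differences". It names no covariates.

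The available text gives no randomisation, sequence, concealment, stratification, minimisation or matching procedure for this study, and does not say that both groups are enrolled over the same period. Randomised trials are mentioned only in connection with other work, in the section on additional therapy and in the reference list.

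**The concern.** The study exists to compare two devices. Without a rule that takes the choice of device out of the hands of those involved, patients in one group may differ from those in the other in ways that affect break-up time. Likeness on three measured factors removes bias only to the extent that those factors carry the imbalance. Other prognostic factors, a preference for goggles or for a microwaved mask, expected adherence and the period of enrolment would remain open.

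Both directions matter. The hypothesis statement takes a clinically relevant difference as the null, so the study may end in a claim that the devices are similar. Confounding can hide a difference as easily as create one. It also cannot be undone once patients are enrolled.

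**Working it through.** **1. The plan's own figure.** The documents give 60 per group, "Statistically significant difference is based on 0.05 level of significance" and "Type I error rate of 0.05 and power (type II error rate) 0.20" (read here as type II error 0.20, that is 80% power). They give no difference, SD, margin or dropout rate, so 60 can be neither reproduced nor refuted. Solved backwards, with no dropout allowance:

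- SE of a difference in means, in SD units: √(2/60) = 0.183.
- Detectable difference, two-sided: (1.960 + 0.842) × 0.183 = 0.51 SD. One-sided, the same calculation gives 0.45 SD.

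The missing inputs do not affect the point about allocation. The SE is what is needed below.

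**2. Does the planned adjustment reach the primary outcome?** The Analyses section describes break-up time as the average of three stopwatch readings, which is a continuous measure. Logistic regression needs a categorical outcome, and no cut-point is defined. The t and Wilcoxon tests adjust for nothing. Even a suitable model could adjust only for recorded factors, and none is listed.

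**3. False positives under residual bias (inputs assumed, not from the documents).** With no device effect and a residual bias of b SD, the two-sided 0.05 test rejects with probability Φ(b/SE − 1.96) + Φ(−b/SE − 1.96).

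| b (SD) | b/SE | False-positive rate |
|---|---|---|
| 0 | 0 | 5.0% |
| 0.1 | 0.55 | 8.5% |
| 0.2 | 1.10 | 19.5% |

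A bias of this size can arise as b = r × g, where r is the correlation of an unbalanced factor with break-up time and g is its difference between groups in SD. With r = 0.3 and g = 0.3, b = 0.09 and the rate is 7.8%. With r = 0.3 and g = 0.5, b = 0.15 and the rate is 13.0%. With r = 0.5 and g = 0.5, b = 0.25 and the rate is 27.8%. Letting r run from 0.3 to 0.5 and g from 0.3 to 1.0 gives anything from 7.8% to 78.2%, so the answer depends almost wholly on what is assumed.

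**4. Masking, on the same assumptions.** Suppose the true difference is 0.5 SD. Power at 60 per group without bias is 78.2%. A bias of 0.1 SD in the opposite direction leaves 0.5 − 0.1 = 0.4 SD and 59.1% power. A bias of 0.2 SD leaves 0.3 SD and 37.6%.

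**5. With randomisation.** The number per group is unchanged, expected bias from allocation is zero, and the false-positive rate with no device effect is the nominal 5%.

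**The case against.** The strongest reply is that silence is not a statement. The design is introduced as a summary, and an aim of balance on severity, age and gender is what one might write before stratified randomisation or minimisation. The title page and the text after the heading Originality and Scientific/Clinical Value were not available for this review, so a design label there cannot be excluded. This stands, and it limits the claim to what is not specified. It does not remove the point: the design and statistical sections, where the method belongs, are present and give none. Even if randomisation is intended, sequence and concealment still have to be stated.

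A reader might infer several stronger things that the documents do not support:

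- **That the study is non-randomised, or that the clinician picks the device.** Nothing says who allocates or how. These are possibilities that the wording leaves open.
- **That season biases the comparison.** A seasonal change over 6 months affects both groups alike unless they are filled at different times. Nothing says that they are, and no figure supports a seasonal effect.
- **That the conditions listed in the background (such as rosacea, Demodex and hypertension) are established confounders.** The protocol itself says that causal links are unproven, and it does not say that these conditions predict break-up time or response to heat. Balancing age and gender would partly cover menopause, and the exclusion of ocular allergy and autoimmune disease narrows the variation.
- **That a difference would say nothing about the devices.** A non-randomised comparison gives weaker attribution, not none. If severity means the DEWS score, which includes break-up time, balancing it would partly balance the primary measure at baseline.

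**Conclusion.** The point holds as a failure to specify. The only rule for forming the groups is an aim of comparability on three factors. Followed exactly as written, it permits allocation by choice or in sequence. The sole between-device comparison is then open to confounding, and the planned logistic regression cannot close the gap for a continuous primary outcome or for unmeasured factors.

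The size of any bias in this study is unknown. The rise from 5% to about 8.5% to 19.5% rests on an assumed residual bias of 0.1 to 0.2 SD and a two-sided test. It shows that a modest bias would matter at 60 per group, not that a bias of that size is present. The point should be settled before enrolment.

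**What to change.** Replace the comparability sentence under Study Design with a statement covering the following:

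- Patients are randomised 1:1 and concurrently to the two devices from a computer-generated sequence. Use either randomly varying blocks stratified by baseline severity, or minimisation with a random element on severity, age and gender. Name the severity measure.
- Allocation stays concealed until eligibility and all baseline examinations are recorded.

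In the statistical section, analyse break-up time with a linear model adjusted for baseline break-up time, severity, age and gender. This keeps all three factors that the protocol wants balanced.

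**Cost.** A few protocol sentences, with no extra patients, visits or assessors. Device choice is given up, and the sequence must be held away from the person enrolling, for example in the existing electronic record system or in sealed envelopes.

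**If allocation is deliberately non-random,** label the study as a non-randomised comparison, pre-specify the confounders and the adjustment method, and limit causal wording in the conclusions.
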